9.5 INTERIM MONITORING PLAN

For purposes of the 6-month analysis, a trend for benefit would be an outcome that does not exclude a significant result being achieved at the end of Phase 2 with a twelve month outcome as specified by the protocol. Changes from baseline in stimulated C-peptide mean AUC in T1D patients on placebo have been reported as approximately 30% at 6 months ([Orban et al 2011](#)³⁹, [Raz et al 2007](#)¹⁹⁴). Sample size calculations were thus based on the assumption of a ~30% treatment effect at around 6 months of treatment and a standard deviation for baseline- and placebo-adjusted stimulated C-peptide mean AUC of 0.39 nmol/liter/2h (Greenbaum et al 2012). In this case, an interim analysis will calculate the conditional power after 21 participants have been evaluated. Based upon the table that follows, should the calculated interim Z value be greater than or equal to 0.8, the conditional power would be estimated to be at least .26 and .74 if the true effect is as assumed under the alternative hypothesis at study conclusion. Therefore, a threshold will be set on the conditional power as the level-of-proof that the difference in stimulated C-peptide mean AUC between gleevec and placebo is of presumed benefit to allow the study to move forward to phase two.

Table of Conditional Power Assuming an Alternate Effect Size (defined as $(\mu_1 - \mu_0)/2(sd) = 0.37$, an interim analysis at 21 patients and a final analysis at 66 patients. Two-tailed alpha = 0.05

Interim Z Value	Conditional Power	Conditional Power
	Under Observed Trend	Under Protocol Assumed Effect
0.0	<.01	.54
0.4	.06	.65
0.8	.26	.74
1.2	.58	.82
1.6	.86	.89

Additional interim analyses will be conducted when 50% of the targeted number of study subjects have reached the planned end point (i.e., one year of follow up) and will be reviewed by the Data and Safety Monitoring Board (DSMB) for assessment of effectiveness and safety. If a group sequential stopping boundary is crossed, the DSMB may recommend termination of the trial early. The Lan-DeMets¹⁹⁵ spending function with an O'Brien-Fleming boundary will be used to protect the type I error probability for the primary outcome analyses, and to assess the significance of the interim results

periodically during the trial. The spending function that approximates the O'Brien-Fleming boundaries is:

$$\alpha_1(t^*) = 2 - 2\Phi\left[\frac{Z_{\alpha/2}}{\sqrt{t^*}}\right]$$

where t^* is the information fraction ($0 < t^* \leq 1$), α_1 is the α -level of the interim (one-sided) test and α is the over-all type I error.

The DSMB will also consider early termination due to absence of a treatment effect (i.e. futility) based on the method suggested by Ellenberg et al¹⁹⁶. The stopping rule is: if the t-test (as described in the primary analysis and positive values reflect a higher values among the experimental group) is less than or equal to 0 at $t^* \geq 0.5$, the study should be stopped based on the futility of rejecting the null hypothesis at the completion of the trial. Simulation studies conducted confirmed that this rule combined with the Lan-DeMets stopping rules have negligible effect on the type I and II error probabilities. Additional analysis will assess potential adverse outcomes of treatment and will assess the incidence of all severe adverse events.

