6.2 RANDOM ASSIGNMENT, BLINDING, AND UNBLINDING

6.2.1 Random Assignment

Participants who sign the informed consent and meet the eligibility criteria will be randomly assigned in a 2:1 ratio to either the experimental or control group. A central automated randomization system will be used for treatment assignment and to create a unique identifier for each new study participant. Random assignment will be stratified according to site.

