9.1 PRIMARY OUTCOME AND ANALYSES

The primary outcome of each participant is the area under the stimulated C-peptide curve (AUC) over the first 2 hours of a 4-hour mixed meal glucose tolerance test conducted at the one-year visit. The AUC is computed using the trapezoidal rule that is a weighted sum of the C-peptide values over the 120 minutes. By the mean value theorem of integral calculus, the weighted mean C-peptide in pmol/mL is simply AUC/120.

The primary statistical hypothesis to be assessed in the study is whether:

- The mean C-peptide value for study subjects receiving imatinib is significantly higher than the mean value for placebo subjects.

The primary analysis will employ the weighted mean derived from the 2 hour AUC for each participant transformed as $\log(\text{mean C-peptide}+1)$. The comparison between the two treatment arms will be based on a t-test of treatment effect in an ANCOVA model adjusting for gender, baseline age and baseline $\log(\text{C-peptide}+1)$ ¹⁹⁰.

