9.4 SAMPLE SIZE AND POWER CALCULATIONS

The primary analysis will compare the difference between the treated group versus the placebo group in the levels of the 2 hour AUC-mean using the $\log(\text{mean C-peptide}+1)$ in an ANCOVA model adjusting for gender, baseline age, and baseline $\log(\text{C-peptide}+1)$. Estimates of $\log(\text{mean C-peptide}+1)$ and root mean square error (RMSE) in the placebo group were obtained from prior studies. Among subjects with baseline C-peptide > 0.2 pmol/ml and age ≤ 21 years, the mean $\log(\text{C-peptide} + 1)$ values is 0.306 with RMSE = 0.185.

The planning parameters for the protocol were based upon the inclusion of adults and children. Unfortunately, the FDA has declined the request to lower the age and, therefore, the study will only enroll adults at this time.

Hence, it is appropriate to revisit the design of the study in light of restricting the eligible population to be age 18 and over. In previous studies, it has shown the older a participant is, the lower the rate of C-peptide loss. This means that the current design of detecting a one-year C-peptide projected level 45% greater than expected on the control arm corresponds to an increase in C-peptide over the baseline value at enrollment, which is not practical. However, analyses completed after this study was initially designed indicate that the appropriate variance estimate to use for the sample size calculation should be smaller than what was used in the current design. This has the net effect of increasing the sensitivity of the trial to detecting an effect size smaller than the advertised value in the current design.

Using standard equations for the comparison of two means, a sample size of 40 Imatinib treated and 20 placebo treated subjects with complete data needed for the primary analysis, would provide power of 85% to detect a 0.35 increase in the mean $\log(\text{C-peptide} + 1)$ (0.306 vs. 0.445, which corresponds to 75% of the RMSE) in the experimental treatment group using a two-sample T- test at the 0.05 level (one-sided).

Assuming that 10% of the subjects will have missing data (one-year MMTT was not done or subject withdrew prior to the one-year assessment), the sample size goal for

this study is 66 subjects (46 + 22). Should the number with missing data exceed 10%, the study will enroll additional replacement subjects as needed.

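### The conditional-power table in 9.5 uses two-tailed 0.05 and 66 analysed patients, but 9.4 plans a one-sided 0.05 test on 40 + 20 complete cases; at Z = 0.8 the planned trial gives about .35/.76, not .26/.74

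*Combined protocol and SAP*

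**What the plan says.** Section 9.5 plans a look after 21 participants. Its table is labelled "an interim analysis at 21 patients and a final analysis at 66 patients. Two-tailed alpha = 0.05" and takes an effect of (μ1 − μ0)/(2 sd) = 0.37. From it the text concludes that "should the calculated interim Z value be greater than or equal to 0.8, the conditional power would be estimated to be at least .26" under the observed trend and .74 under the assumed effect. It then says that "a threshold will be set on the conditional power as the level-of-proof" for the study to move forward. Section 3.1 says the efficacy assessment at this look is for the DSMB and FDA.

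The final analysis is described differently elsewhere:

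- 9.4 bases power on "a sample size of 40 Imatinib treated and 20 placebo treated subjects with complete data needed for the primary analysis", using a "test at the 0.05 level (one-sided"). There, 66 is the enrolment goal after allowing for 10% missing data.
- 9.1 states a directional hypothesis: the imatinib mean "is significantly higher than the mean value for placebo subjects".
- 6.2.1 has participants "randomly assigned in a 2:1 ratio to either the experimental or control group".
- 9.5 itself, in defining the spending function, refers to the "level of the interim (one-sided) test".

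**The concern.** Conditional power depends on the final critical value, the information fraction and the drift at full information. The table's critical value (two-tailed 0.05) and its final number (66) both conflict with 9.4. Its drift appears to assume equal arms although the trial is 2:1. It also ignores the spending function that 9.5 adopts for the primary outcome.

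The errors run in opposite directions. A one-sided test raises conditional power, while 60 patients and 2:1 allocation lower it, so the net effect cannot be seen without calculation. What is at stake is whether the two lower bounds quoted at Z = 0.8 are true. A further question is whether a cut at Z = 0.8 and a cut on the printed conditional power are the same rule in the trial that will be run.

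**Working it through.** **Formula.** With information fraction t, final critical value c and drift θ (the expected final Z),

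CP = Φ[(Z√t + θ(1 − t) − c) / √(1 − t)].

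Observed trend: θ = Z/√t, so allocation does not enter. Assumed effect: θ = δ/√(1/n₁ + 1/n₀), with δ the standardised difference. The table's 0.37 is half of δ, so δ = 0.74. Section 9.4 gives (0.445 − 0.306)/0.185 = 0.139/0.185 = 0.751.

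**1. Reproduce the printed table.** t = 21/66 = 0.318 and c = 1.96. With equal arms of 33, θ = 0.74/√(2/33) = 0.37√66 = 3.006.

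| Z | Trend, computed | Trend, printed | Assumed, computed (equal arms) | Assumed, printed | Assumed, if 2:1 (44 + 22, θ = 2.834) |
|---|---|---|---|---|---|
| 0.0 | .009 | <.01 | .543 | .54 | .487 |
| 0.4 | .065 | .06 | .649 | .65 | .595 |
| 0.8 | .256 | .26 | .744 | .74 | .696 |
| 1.2 | .580 | .58 | .823 | .82 | .784 |
| 1.6 | .856 | .86 | .885 | .89 | .855 |

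All ten cells agree with the print to within rounding. The 2:1 column matches no printed cell. Equal allocation is therefore inferred from the numbers; the plan does not state it.

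**2. Which test does 9.4 use?** Noncentral-t power for 40 + 20 at 0.751 SD is 85.7% at one-sided 0.05 and 77.0% at two-sided 0.05. Only the one-sided test gives the stated 85%.

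**3. Final bound under the spending function.** Take one look at t* = 0.5.

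- Overall one-sided 0.05: the printed function spends 2 − 2Φ(1.96/√0.5) = 0.00557. The first bound is 2.538 and the final bound 1.662.
- Two-sided 0.05: 0.00279 per tail. The first bound is 2.772 and the final bound 1.979.

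**4. Replace the inputs one at a time at Z = 0.8 (δ = 0.74).** For 60 patients, t = 21/60 = 0.35 and θ = 0.74√(40·20/60) = 2.702.

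| Inputs | c | Trend | Assumed |
|---|---|---|---|
| As printed: two-sided, 66, equal arms | 1.960 | .256 | .744 |
| Two-sided, 66, 2:1 | 1.960 | .256 | .696 |
| Two-sided, 60, 2:1 | 1.960 | .225 | .631 |
| Two-sided, 60, 2:1, spending-adjusted | 1.979 | .218 | .622 |
| One-sided, 60, 2:1 | 1.645 | .358 | .766 |
| One-sided, 60, 2:1, spending-adjusted | 1.662 | .350 | .759 |

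For the last row, assumed effect: (0.8 × 0.592 + 2.702 × 0.65 − 1.662)/√0.65 = 0.567/0.806 = 0.704, and Φ(0.704) = .759.

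**5. Sensitivity to the effect.** One-sided and spending-adjusted, at Z = 0.8, the assumed-effect figure is .67 at 0.65 SD, .72 at 0.70, .77 at 0.75 and .81 at 0.80. It reaches .74 at about 0.72 SD.

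**6. Z values that match the printed figures.** One-sided, adjusted, 0.74 SD: conditional power of .26 under the trend corresponds to Z = 0.68, and .74 under the assumed effect to Z = 0.72. Neither is 0.8.

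**The case against.** The strongest reply is that nothing is shown to go wrong. The text speaks of Z of at least 0.8 and of conditional power of at least .26 and .74. Under the one-sided test of 9.4 that sentence is true, and in the assumed-effect column the shortfall is about two points. The interim analysis will calculate conditional power from the data, so the table may be only illustrative, and no numeric threshold is explicitly fixed. The two cuts differ only if someone applies the printed .26 or .74 to a recomputed conditional power. Section 9.4 also reports that the FDA declined to lower the age, which removes part of what the 21-patient look was meant to inform.

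The replacement figures have weaknesses too. The 0.75 SD comes from subjects aged 21 or under, and 9.4 itself doubts those planning values for adults. The calculation, like the table, treats a 6-month result as partial information on the 12-month endpoint, and the documents give no correlation between the two. As an illustration, assume equal standardised effects at both times and correlation ρ. Then CP = Φ[(θ + ρ√t(Z − θ√t) − c)/√(1 − ρ²t)], and the .76 becomes about .77 at ρ = 0.8 and .81 at ρ = 0.4. That is as large as the correction to that column.

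Most of this stands as a limit on size and precision, and it is why the point is minor. It does not remove the contradiction: 9.4 and 9.5 disagree in print on sidedness and on the number analysed, and the truth of the quoted bounds depends on which is right. The interim rule is still in 9.5.

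**Conclusion.** The point holds and is minor. The table is computed correctly from inputs that differ from the planned trial in alpha, in the number analysed and, by inference, in allocation.

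- **If the one-sided test of 9.4 governs**, the error is conservative: about 9 to 10 points in the trend column and 2 to 3 points in the assumed-effect column at Z = 0.8. The .74 bound holds only for standardised effects of about 0.72 or more.
- **If the table's two-tailed 0.05 governs**, both bounds fail, the assumed-effect one by about 11 to 12 points, and the power in 9.4 is about 77%.

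These results assume 40 + 20 analysed, a single look at half the information for the adjusted bounds, and the table's own treatment of 6-month data as information on the 12-month outcome. Reproduction of the table and the conflict between sections are certain. The figure of .35/.76 is what the table's own method gives with the trial's inputs, and is no firmer than that method.

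**What to change.** 1. State one sidedness in 9.4 and 9.5. If two-sided 0.05 is chosen, restate the 9.4 power as about 77%.
2. Recompute the table with 2:1 allocation, 60 evaluable patients, the spending-adjusted final critical value and a named effect. For one-sided 0.05, c = 1.662 and 0.75 SD, the rows are:

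| Z | Observed trend | Assumed effect |
|---|---|---|
| 0.0 | .020 | .558 |
| 0.4 | .111 | .670 |
| 0.8 | .350 | .768 |
| 1.2 | .675 | .848 |
| 1.6 | .902 | .907 |

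3. Restate the conditional power attached to Z of at least 0.8, and say whether the threshold is on Z or on conditional power.
4. Say where the effect comes from. Section 9.5 describes an effect of about 30% at around 6 months and does not derive 0.37 from 9.4, although 2 × 0.37 = 0.74 SD is close to the 75% of RMSE given there.
5. Say that 6-month results are being used as partial information on the 12-month endpoint.

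The cost is a short recalculation and a few sentences in 9.5. Sample size and conduct are unchanged under the one-sided test; only a two-sided choice requires the 9.4 power to be restated.

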10. ACCESS TO SOURCE DATA/DOCUMENTS

The investigational sites participating in this study will maintain the highest degree of confidentiality permitted for the clinical and research information obtained from participants in this clinical trial. Medical and research records should be maintained at each site in the strictest confidence. However, as a part of the quality assurance and legal responsibilities of an investigation, the investigational sites must permit authorized representatives of the sponsor, and health authorities to examine (and to copy when required by applicable law) clinical records for the purposes of quality assurance reviews, audits, and evaluation of the study safety and progress. Unless required by the laws permitting copying of records, only the coded identity associated with documents or other participant data may be copied (and any personally identifying information must be obscured). Authorized representatives as noted above are bound to maintain the strict confidentiality of medical and research information that may be linked to identified individuals. The investigational sites will normally be notified in advance of auditing visits.

11. QUALITY CONTROL AND QUALITY ASSURANCE

The investigator is required to keep accurate records to ensure that the conduct of the study is fully documented. The investigator is required to ensure that all CRFs are completed for every participant entered in the trial.

The sponsor is responsible for regular inspection of the conduct of the trial, for verifying adherence to the protocol, and for confirming the completeness, consistency, and accuracy of all documented data.

The CRFs will be completed online via a web-based electronic data capture (EDC) system that has been validated and is compliant with Part 11 Title 21 of the Code of Federal Regulations. Study staff at the site will enter information into the electronic CRFs, and the data will be stored remotely at a central database. All elements of data entry (i.e., time, date, verbatim text, and the name of the person performing the data entry) will be recorded in an electronic audit trail to allow all changes in the database to be monitored and maintained in accordance with federal regulations.

Study staff will enter data from a study visit on the relevant eCRFs within 14 days following the visit or the time when data becomes available.

12. ETHICAL CONSIDERATIONS AND COMPLIANCE WITH GOOD CLINICAL PRACTICE

12.1 STATEMENT OF COMPLIANCE

This trial will be conducted in compliance with the protocol, current Good Clinical Practice (GCP) guidelines—adopting the principles of the Declaration of Helsinki—and all applicable regulatory requirements.

Prior to study initiation, the protocol and the informed consent documents will be reviewed and approved by the sponsor and an appropriate ethics review committee or institutional review board (IRB). Any amendments to the protocol or consent materials must also be approved by the Sponsor, the IRB and submitted to FDA before they are implemented.

12.2 INFORMED CONSENT

The informed consent form is a means of providing information about the trial to a prospective participant and allows for an informed decision about participation in the study. All participants (or their legally acceptable representative) must read, sign, and date a consent form before participating in the study, taking the study drug, and/or undergoing any study-specific procedures.

The informed consent form must be updated or revised whenever important new safety information is available, whenever the protocol is amended, and/or whenever any new information becomes available that may affect participation in the trial.

A copy of the informed consent will be given to a prospective participant for review. The study investigator will review the consent and answer questions. The participant will be informed that participation is voluntary and that he/she may withdraw from the study at any time, for any reason.

12.3 PRIVACY AND CONFIDENTIALITY

A participant's privacy and confidentiality will be respected throughout the study. Each participant will be assigned a sequential identification number. This number, rather than the participant's name, will be used to collect, store, and report participant information.

13. PUBLICATION POLICY

The JDRF policy on publication of study results will apply to this study.

Appendix 1. Schedule of Events

Week	-3 to -4	0	2	4	9	13	17	22	26	39	52	78	104
Visit	-1	0	1	2	3	4	5	6	7	8	9	10	11
GENERAL ASSESSMENTS													
Informed consent	X												
Eligibility criteria	X												
Medical history	X												
Adverse events	X	X	X	X	X	X	X	X	X	X	X	X	X
Concomitant medications	X	X	X	X	X	X	X	X	X	X	X	X	X
Physical examination ¹	X	X		X	X	X			X		X	X	X
Secondary sexual characteristics ²		X									(X)		(X)
Vital Signs	X	X	X	X	X	X	X	X	X	X	X	X	X
Pregnancy Monitoring (if applicable)	X	X		X	X	X	X	X	X		X	X	X
ECG	X		X										
LABORATORY ASSESSMENTS													
Serum chemistries and liver panel ³	X	X	X	X	X	X	X	X	X	X	X	X	X
Autoantibodies	X												
Hematology ⁴	X	X	X	X	X	X	X	X	X	X	X	X	X
Infectious disease serology ⁵	X												
PPD skin test or IGRA	X												
Urine hCG	X	X		X	X	X	X	X	X		X	X	X
Urinalysis	X								X		X		X
Prostate Specific Antigen (males only)		X							X		X		X
C-peptide levels (tested from MMTT) ⁶	X					X			X		X	X	X

¹Excluding genitalia unless clinically indicated

² The Tanner stages will be assessed at the baseline visit for every participant under 18 years of age. After the baseline visit, Tanner stages will be assessed annually on all participants who are < stage 3. If the Tanner stage is ≥ 3 at the baseline visit or any subsequent visit, Tanner stages will not need to be assessed at any future visit.

³ To include sodium, calcium, potassium, chloride, phosphate, total CO₂, BUN, creatinine, AST, ALT, alkaline phosphate, direct and total bilirubin.

⁴ Performed locally; to include CBC with differential and platelets.

⁵ Hepatitis B and C, HIV, toxoplasmosis, VZV, EBV, and CMV serology. CMV/EBV PCR testing may be obtained (centrally) or locally, if necessary to confirm active infection.

⁶ 4-hour MMTT at Visits -1, 9, 11 and 2-hour MMTT at Visits 4, 7, and 10.

Week	-3 to -4	0	2	4	9	13	17	22	26	39	52	78	104
Visit	-1	0	1	2	3	4	5	6	7	8	9	10	11
Plasma Glucose (tested from MMTT) ⁵	X					X			X		X	X	X
HbA _{1c} levels	X					X			X	X	X	X	X
STUDY DRUG ADMINISTRATION													
Study drug administration		X	X	X	X	X	X	X	X				
Study drug compliance			X	X	X	X	X	X	X				
DISEASE SPECIFIC ASSESSMENTS													
Glucose (Glucometer Reading)		X	X	X	X	X	X	X	X	X	X	X	X
Insulin use		X	X	X	X	X	X	X	X	X	X	X	X
Hypoglycemia assessment		X	X	X	X	X	X	X	X	X	X	X	X
Serum-Adiponectin ⁷		X		X					X		X		X
Plasma-Glucagon ⁶	X					X			X		X	X	X
Plasma-Proinsulin ⁶	X					X			X		X	X	X
BONE AND MINERAL METABOLISM													
Serum Calcium ⁸		X		X		X			X		X		
Serum Phosphate ⁷		X		X		X			X		X		
PTH		X		X		X			X		X		
25-OH Vitamin D		X									X		
Serum CTX ⁹		X				X			X		X		
Osteocalcin ⁸		X				X			X		X		
GROWTH RATE ASSESSMENTS ¹⁰													
Plain Radiograph of Left Hand		X									X ¹¹		X ¹⁰
Height by Stadiometer ¹²	X	X	X	X	X	X	X	X	X	X	X	X	X
Arm span		X							X		X		X

⁷ Samples will be archived for potential future testing.

⁸ Tested as part of serum chemistry panel.

⁹ Samples will be archived and tested if clinically indicated.

¹⁰ To be performed on growing-age participants per Section 5.2.9.

¹¹ Bone age will be assessed annually until epiphyses are near complete closure (98% of mature height at bone age of 15 yrs 9 months for boys, 14 yrs for girls).

¹² Subjects will need to be measured with a wall mounted stadiometer to insure accurate height measurements.

Week	-3 to -4	0	2	4	9	13	17	22	26	39	52	78	104
Visit	-1	0	1	2	3	4	5	6	7	8	9	10	11
IGF-1, IGF-BP3, LH, FSH, Estradiol (females), Testosterone (males) ¹³		X							X		X		X
Total IgA		X ¹⁴											
TSH and T4		X ¹³									X ¹⁵		X ¹⁴
Tissue transglutaminase (IgA) ¹⁶		X ¹³									X ¹⁴		X ¹⁴
MECHANISTIC ASSAYS													
Serum-Autoantibody Analysis		X		X		X			X		X		X
PBMC-Flow Cytometry Panel Staining		X		X		X			X		X		X
PBMC-Cell Based Assays		X		X		X			X		X		X
PBMC-Genomics, Proteomics		X		X		X			X		X		X
PBMC- FOXP3 Methylation Assay		X		X		X			X		X		X
Whole Blood-Gene Expression Profiling		X		X		X			X		X		X
Whole Blood DNA-HLA Genotypes		X				X					X		
Plasma-Archive		X		X		X			X		X		X
Serum- Beta Cell Death Assay		X	X	X	X				X		X		X
Serum-Cytokines		X	X	X	X				X		X		

¹³ Samples will be archived and tested if clinically indicated.

¹⁴ Tested at Baseline only if not tested by referring physician within 3 months prior to Baseline.

¹⁵ Samples will be collected at Visits 9 and 11 only if clinically indicated in growing age participants. If required, testing will be performed real-time.

¹⁶ Performed locally.

